-Months 18-20: Second round of data analyses by Statistician (supervised by PI): CPRD/HES data for WP1-3 in Months 18-19, and Danish dataset for WP4 in Month 20.

-Months 21-30: Data analysis of renal outcomes using CPRD and HES data.

-Month 30: Internal discussion of final study results and dissemination plan, and coinvestigators meeting, organised by PC (supervised by PI).

-Months 31-33: Writing of study report (PI, PC), related abstracts/manuscripts (PI, Statistician, and coinvestigators), dissemination to lay audience, and study closure

REGULAR COMMUNICATION

A Steering committee formed by an external chair, the study PI, PPI representatives, a pharmacoepidemiologist, and a clinician will meet in November 2016, May 2017, and May 2018 to evaluate the study progress and adherence to governance policies.

A Study Investigators Group constituted by the PI, all study co-applicants (including PPI representatives) and international collaborators will have regular meetings/teleconferences every 3 months to ensure effective communication between investigators at different sites, and to monitor study progress.

There will be:

• Five Co-applicants and external collaboration meetings: months 1, 10, 17, 30 and 33 ('kick-off'

meeting, 'data management discussion' meeting, 'internal discussion on preliminary results' meeting, 'final results and dissemination plan' meeting and 'study closure' meeting).

• Co-applicants and external collaborators teleconferences: when no meeting is planned, a teleconference will be held every 3 months.

More meetings will be planned if necessary.

APPROVAL BY ETHICS COMMITTEES

The proposed study will only use retrospective, routinely collected data. The identified data sources (CPRD, HES, and the Odense University Hospital Database) do not request ethics committee approval to access/extract their data. Instead, approval by internal independent data access committees is required, including the Independent Scientific Advisory Committee (ISAC) at MHRA for CPRD and linked HES data.

We have wide experience in the submission (and subsequent approval) of protocols to ISAC: the PI has been successfully approved 4 protocols for different studies, and other listed coapplicants like [name] and [name] have obtained approval for 3 and 2 protocols respectively. In addition, support will be available from internal investigators for each of the identified data sources, who are listed co-applicants in this grant or external collaborators ([name], consultant endocrinologist and professor, and [name], medical director of the Odense University Hospital).

Addendum: A first application to the Confidentiality Advisory Group (CAG) for the linkage of CPRD data to the UK Renal Registry was rejected. Following from this, an ad-hoc application (for a one-off linkage for this piece of research) was submitted for approval from the Research Ethics Committee (Oxford C REC) and CAG, which were both approved in March/2017.

An application was submitted to NHS Digital in August/2017 to act as a third trusted party in the linkage of CPRD and UK Renal Registry data. In June/2018 it was decided that, given the relevance of the preliminary study results, the final results of the study will be obtained using data from the CPRD linked to HES, as the NHS Digital application to link the CPRD and the UK Renal Registry was still pending approval. This has been discussed with and approved by the NIHR HTA.

PATIENT AND PUBLIC INVOLVEMENT

The proposed study affects mainly patients with osteoporosis and chronic kidney disease, and two charities provide the natural environment for the dissemination of our results to the target lay audience: the National Osteoporosis Society (NOS), and the National Kidney Federation (NKF). Two key patient and public representatives have been identified and included as co-applicants of the current proposal from its early stages: [name], health sector relations manager at the NOS, and [name], patient representative and executive member at the NKF. The overarching aims of their involvement are: 1.to assist the study investigators in identifying the most relevant study outcomes (adverse events) from a patients' perspective, 2.to collaborate in the drafting of the grant lay summary, 3.to participate in the study steering committee to monitor and discuss study progress and preliminary results, and 4.to organize dissemination to the lay audience.

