DISSEMINATION AND PROJECTED OUTPUTS
OUTPUTS
DISSEMINATION
MANAGEMENT PLAN
REGULAR COMMUNICATION
APPROVAL BY ETHICS COMMITTEES
PATIENT AND PUBLIC INVOLVEMENT26
REFERENCES
APPENDIX 1

SUMMARY OF RESEARCH

AIM/S

Although osteoporosis and fragility fractures are common amongst CKD patients, the effectiveness and safety of first-line anti-fracture therapies (bisphosphonates) for this population are still unclear. We therefore aim to study the association between oral bisphosphonate (OB) use in stage ≥3B CKD patients and the following outcomes: CKD progression (stage worsening or entering renal replacement therapy or transplant) (WP1), clinical fracture/s (WP2), adverse events (hypocalcaemia or hypophosphatemia, upper gastro-intestinal events, and acute kidney injury) (WP3), and axial bone mineral density (WP4).

METHODS

Data sources: the primary data source for WP1-3 of our study will be the Clinical Practice Research Datalink (CPRD), linked to the Hospital Episodes Statistics (HES). Data from the Danish Odense University Hospital Database (OUHD) will be used for WP4.

Study participants: all patients registered in CPRD or in OUHD, aged \geq 40 years, with an eGFR<45, and with \geq 1 years of follow-up data available will be included. Users of bisphosphonates in the year before eGFR testing, as well as CPRD participants with no possible linkage to HES data will be excluded.

Exposure: Users of oral bisphosphonates will be identified from primary care prescriptions (CPRD) or pharmacy dispensations (OUHD).

Outcomes: WP1: CKD progression will be defined as stage worsening (according to eGFR as recorded in CPRD) or initiation of renal replacement therapy/transplant (HES).

Study outcomes for WP2-3 will be ascertained using previously validated lists of READ/OXMIS (CPRD) (1-3) or ICD-10/OPCS (HES) (4) codes. The main study outcomes will be: all clinical fractures excluding the skull/face and digits, which are not considered to be osteoporotic (WP2), and adverse events (hypocalcaemia/hypophosphatemia requiring hospital admission, upper gastro-intestinal events, and hospitalization for acute kidney injury) for WP3. WP4: annualized hip bone mineral density percentage change, as measured using DXA scan, will be measured.

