The chosen study design is a propensity score-matched retrospective cohort study. This is one of the best pharmaco-epidemiological designs available for the assessment of intended (benefits) and unintended (risks) effects of drugs in observational data. Propensity score-matching will therefore be used to match each eligible bisphosphonate user to 5 non-users, producing matched comparable (in terms of observed baseline characteristics) cohorts.

TARGET POPULATION

The target population of this study will be patients with an eGFR<45 (based on serum creatinine) aged 40 years or older at the age of biochemistry testing.

EXCLUSION CRITERIA

From the population described above, we will exclude those with any of the following exclusion criteria:

- Less than 1 year of follow-up data available within the data source/s.
- CPRD participants with no possible linkage to HES.
- Use of anti-osteoporosis medication/s in the previous year (except calcium and/or vitamin D supplements).
- Use of any (except calcium and/or vitamin D supplements) other anti-osteoporosis medication/s (other than bisphosphonates).

SETTING/CONTEXT

Setting: The proposed study will obtain data from both primary (CPRD) and secondary (HES) care.

Study period: Currently used oral bisphosphonates (alendronate, risedronate and ibandronate) were approved and launched to the market in 1996 onwards. Our study period will therefore cover from 1996 to the latest data extraction for the identified data sources, likely 31/12/2014.

Follow-up: Data from randomized placebo-controlled trials have shown that bisphosphonates are effective to reduce fracture risk only after at least 6 months of continuous use (27). That is not the case though for adverse events, which can be observed immediately after bisphosphonate therapy initiation (14, 17, 28). Therefore, different follow-up windows will be established, as follows:

- Safety outcomes (WP1 and WP3): Patients will be followed from the latest of the following dates
- a) Start of study period
- b) One year of valid data in database
- c) Date of incident prescription of bisphosphonate (after one year of non-use)

until the earliest date of:

- a) The end of enrolment in the database (due to moving out or death)
- b) Date of last data update in the database
- c) Stopping of treatment +30 days (no repeat prescription within 1 month)
- d) Switch of treatment to other (non-bisphosphonate) osteoporosis medication

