- e) Outcome of interest (different date for each study outcome)
- Effectiveness outcomes (WP2 and WP4): Patients will be followed from the latest of the following dates
- a) Start of study period
- b) One year of valid data in database
- c) Date of continued prescriptions of an oral bisphosphonate for 6 months after the date of therapy initiation

until the earliest date of:

- a) The end of enrolment in the database (due to moving out or death)
- b) Date of last data update in the database
- c) Stopping of treatment +180 days (no repeat prescription within 6 months)
- d) Switch of treatment to other osteoporosis medication, with no repeat prescription of oral bisphosphonates within the next 6 months
- e) Incident recorded fracture (WP2) or last BMD measurement available (WP4)

SAMPLING

One of the advantages of routinely collected datasets is that the contained information is readily available, not needing active recruitment. Therefore, all patients eligible (see target population and exclusion criteria above) registered in the chosen data sources will be included.

Sample size/power: According to feasibility counts provided by CPRD, the number of eligible patients (with an eGFR<45 and possible to link to HES) would be of 204,528 subjects, and 34,127 (16.7%) of these received oral bisphosphonate prescriptions. These numbers would provide statistical power to reliably answer each of the study aims, as it can be seen below:

Work-package 1: In a survival analysis (log-rank 2-sided test), accepting 5% type I error and 20% attrition from propensity score matching and loss to follow-up in 2 years, and assuming CKD stage progression rates of 12/100 person-years (29), the available number of participants would provide 90% power to detect an excess risk of CKD progression of 10% or more (HR \geq 1.10) associated with oral bisphosphonate use.

Work-package 2: In a log-rank (2-sided) test, and accepting 5% type I error and 20% drop-out, with 2 years of follow-up and an expected fracture rate of 103/10,000 person-years in CPRD data (30), the available sample size would provide 90% power to detect a fracture reduction of at least 15% (HR≤0.85) amongst oral bisphosphonate users (compared to non-users).

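### WP1 does not exclude patients already on maintenance dialysis, although its outcome includes starting renal replacement therapy

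*Protocol*

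**What the plan says.** Protocol, Target population: the study takes "patients with an eGFR<45 (based on serum creatinine) aged 40 years or older". No lower eGFR limit is set.

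Protocol, Exclusion criteria: "From the population described above, we will exclude those with any of the following exclusion criteria". Four items follow: under one year of data, no possible HES linkage, anti-osteoporosis medication in the previous year, and use of any other anti-osteoporosis medication. The Summary's description of participants adds nothing on kidney treatment.

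Protocol, Sampling: "all patients eligible (see target population and exclusion criteria above) registered in the chosen data sources will be included". The feasibility count is described in the same terms: "the number of eligible patients (with an eGFR<45 and possible to link to HES) would be of 204,528 subjects".

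Protocol, Setting/Context, Follow-up: for WP1 and WP3, follow-up starts at the latest of the start of the study period, one year of valid data, and "Date of incident prescription of bisphosphonate (after one year of non-use"). There is no requirement to be free of the outcome or of renal replacement therapy.

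Protocol, Summary, Outcomes: "CKD progression will be defined as stage worsening (according to eGFR as recorded in CPRD) or initiation of renal replacement therapy/transplant (HES"). The Aims and Objectives likewise describe WP1 as stage worsening or entering renal replacement therapy or transplant.

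**The concern.** The WP1 outcome is an incident event, so its risk set should hold people who can still have it. A maintenance-dialysis patient has already started renal replacement therapy and is normally in the last CKD stage, and creatinine-based eGFR on dialysis does not track progression. (These are general clinical facts, not statements in the Protocol.) The wording of the outcome limits which events count; it does not limit who contributes person-time.

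Two faults follow from the one missing criterion:

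- Person-time from patients who cannot validly have the event enters the WP1 denominators.
- If such a patient is later transplanted, the outcome definition read literally records CKD progression, which misclassifies the event.

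WP1 is the study's kidney-safety question, and the Protocol plans to report both absolute rates and hazard ratios for it.

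**Working it through.** **1. Can a dialysis patient enter WP1 under the rules as written?** Yes. A patient aged 40 or over with a recorded eGFR below 45, a year of data, HES linkage and no anti-osteoporosis drug in the previous year meets every listed rule. The Sampling section includes everyone eligible, and no start rule tests dialysis status.

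**2. The plan's own WP1 figure.** Inputs from Sampling, Sample size/power: 34,127 users, 20% attrition, 2 years, 12 events per 100 person-years, two-sided 5%, HR 1.10; 1:5 matching from Study design. (The Summary prints a different user count; the Data collection section agrees with the figure used here.)

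- Users analysed: 34,127 × 0.8 = 27,302; non-users 5 × 27,302 = 136,508.
- Two-year risks: non-users 1 − exp(−0.24) = 0.2134; users 1 − exp(−0.264) = 0.2320.
- Expected events: about 35,462.
- Events needed for 90% power (Schoenfeld): (1.960 + 1.282)² / [(1/6)(5/6)(ln 1.10)²] = about 8,329.

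The stated 90% holds as a lower bound; power from these inputs exceeds 99.99%.

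**3. Effect on power.** Suppose a share f of the cohort can have no event and the 12/100 rate applies only to the rest. Events become 35,462 × (1 − f):

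| f (assumed) | Expected events |
|---|---|
| 1% | 35,107 |
| 5% | 33,689 |
| 10% | 31,916 |

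All are far above 8,329. Excluding these patients loses no valid events.

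**4. Effect on absolute rates.** If the rate among those truly at risk is 12/100 person-years, the rate over the whole group at the start of follow-up is 12 × (1 − f): 11.88 at f = 1% and 11.40 at f = 5%. This happens whether or not the groups are balanced.

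**5. Effect on the hazard ratio.** At the start of follow-up, with no events among dialysis patients, apparent HR ≈ true HR × (1 − f_users)/(1 − f_non-users), where the shares are those left after matching. For a true HR of 1.00:

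| Users on dialysis (assumed) | Non-users on dialysis (assumed) | Apparent HR |
|---|---|---|
| equal | equal | 1.00 |
| 1% | 2% | 0.99/0.98 = 1.010 |
| 1% | 3% | 0.99/0.97 = 1.021 |
| 1% | 5% | 0.99/0.95 = 1.042 |
| 2% | 1% | 0.98/0.99 = 0.990 |
| 5% | 2% | 0.95/0.98 = 0.969 |

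The documents give none of these shares. Transplants counted as events among dialysis patients would alter these values, in a direction that depends on the group in which they fall.

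**The case against.** The strongest reply is the matching. The analysis is 1:5 matched on a separate propensity score per outcome, built from prespecified predictors of that outcome, with a Cox model stratified by matched set. If dialysis status is balanced, the hazard ratio is not biased. That stands: the covariate list is not shown, so neither balance nor imbalance can be asserted. Matching does not, however, repair the absolute rates or the misclassified transplants.

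It can also be said that entering or initiating renal replacement therapy presupposes patients not yet on it, and that one exclusion list serves four work packages, so a general exclusion would not suit fracture or bone density. The first describes intent, but the eligibility rules do not carry it out. The second is right and confines the fix to WP1. The planned interaction test by CKD stage is at most a partial check.

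A reader might infer more than the text supports:

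- *Transplant recipients cannot have the outcome either.* A recipient with a functioning graft can worsen in stage or return to dialysis. By its title, the study cited for the 12/100 rate covers transplanted as well as native kidneys.
- *The acute kidney injury outcome has the same fault.* That outcome is "hospitalization for acute kidney injury", and nothing in the documents makes a coded admission impossible on dialysis; graft recipients can have one.
- *The bias runs towards apparent harm and is a large part of the targeted 10% excess.* The Protocol says the drugs are contraindicated at eGFR below 30-35, which makes dialysis plausibly commoner among non-users before matching. It says nothing about the position after matching. A figure near 1.04 is one assumed corner, and the sign can reverse.

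**Conclusion.** The gap is real but confined to maintenance-dialysis patients in WP1. As written, the plan admits them to the risk set of an incident outcome that they have already reached in part and cannot validly reach otherwise, and would count a later transplant as progression. The distortion of WP1 absolute rates follows directly. Hazard-ratio bias is conditional on a difference in dialysis share that survives matching: about 1.01 to 1.04 under a true null for assumed shares of 1% in users against 2% to 5% in non-users, below 1 if reversed, none if equal. Actual size and direction cannot be known from the documents. Power is unaffected. Eligibility is fixed in the Protocol, whose list reads as complete and is followed by inclusion of everyone else, so this is not a detail left to an analysis plan.

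**What to change.** Add one WP1-only criterion: exclude patients on maintenance dialysis at the index date (the date WP1 follow-up starts), identified by a HES or CPRD maintenance-dialysis code on or before that date. Keep prior transplant recipients with a functioning graft. Since many of them will carry an older dialysis code, the rule should not apply where a transplant code follows the dialysis code by the index date and dialysis has not resumed. State their WP1 event as stage worsening or return to dialysis.

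Leave the populations for WP2, WP3 and WP4 as they are.

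Cost: a few lines of text and a slightly smaller WP1 cohort. HES codes for renal replacement therapy and transplant are already needed for the outcome. The approval section's addendum says the final results will use CPRD linked to HES rather than the UK Renal Registry, so the exclusion will be only as complete as the coding in those two sources.

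### Two exclusion criteria have no time anchor at cohort entry and, as worded, conflict with the protocol's own follow-up and censoring rules

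*Protocol*

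**What the plan says.** All of this is in the Protocol.

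- **Exclusion Criteria, first bullet:** excludes patients with "Less than 1 year of follow-up data available within the data source/s". The Summary of Research (Study participants) states the same rule as an inclusion condition of at least "1 years of follow-up data available will be included". Neither place says from which date the year is counted.
- **Exclusion Criteria, third bullet:** "Use of anti-osteoporosis medication/s in the previous year (except calcium and/or vitamin D supplements". This one is limited to a look-back year.
- **Exclusion Criteria, fourth bullet:** "Use of any (except calcium and/or vitamin D supplements) other anti-osteoporosis medication/s (other than bisphosphonates". No period is given.
- **Follow-up, start of follow-up:** the latest of several dates, one of which is "One year of valid data in database".
- **Follow-up, censoring item a (both outcome groups):** follow-up ends when enrolment ends through moving out or death, with no minimum duration.
- **Follow-up, censoring item d, safety outcomes:** "Switch of treatment to other (non-bisphosphonate) osteoporosis medication". The effectiveness list has a similar item, which applies only if no oral bisphosphonate is prescribed again in the following six months.
- **Follow-up, introduction:** adverse events are described as effects "which can be observed immediately after bisphosphonate therapy initiation".

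**The concern.** Eligibility for a cohort should be decided on what is known at entry. What happens later (death, leaving the practice, starting another drug) belongs to censoring or to competing-risk handling. Two of the four exclusion bullets do not respect that line as written, and the follow-up section handles the same events differently.

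Two programmers could therefore build different cohorts from this text. One of those cohorts would be selected on post-entry events that may be related to the outcomes: death after acute kidney injury, or a change of drug after a fracture or an upper gastro-intestinal event. The issue touches WP1 to WP4, because all of them share the exclusion list.

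**Working it through.** No figure in the protocol depends on these criteria, so the check sets the rules side by side.

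**1. First bullet against censoring item a.** Take a patient who starts an oral bisphosphonate with several years of earlier records and dies eight months later.

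- If the year runs after entry, the patient is excluded.
- If the year is a look-back, the patient is eligible.
- Under censoring item a, the patient contributes eight months and is censored at death.

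The first and third lines cannot both operate. The literal reading has support. Elsewhere in the protocol, follow-up means time after entry: the two years in the power calculations, the denominator of the medication possession ratio, and the Follow-up section itself. The look-back reading also has support, because follow-up cannot start until a year of valid data exists and users need a year of non-use before the incident prescription.

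There is a further consequence of the literal reading. The Hazard ratios paragraph moves to Fine and Gray models if mortality differs between groups. With a year of data required after entry, no first-year deaths remain in either group, so that comparison would lack them.

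**2. Fourth bullet against censoring item d.** The third bullet already covers the previous year. To add anything, the fourth must cover use more than a year earlier, use after entry, or both. The text does not choose.

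- If only earlier use is meant, item d works as written.
- If use after entry is included, every switcher is already excluded and item d is empty in both censoring lists. It would also remove patients whom the effectiveness list keeps under follow-up, namely those who take another drug but resume an oral bisphosphonate within six months.

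**3. Non-users.** Item d speaks of a switch of treatment, which a non-user does not have. The comparator is described under Health Technologies Being Assessed as people not on anti-osteoporosis therapy. For a non-user who starts another drug, for example after a fracture, the censoring lists give no clear rule. An open-ended fourth bullet would delete that person, together with the fracture, instead of censoring at the new drug.

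**4. Illustration of the literal first bullet (assumed inputs, none from the protocol).** Let L be the annual probability of dying or leaving without the event, with rate λ = −ln(1 − L). Let first-year events fall uniformly over the year, and let f be the share that are promptly fatal. The share of first-year events removed is f + (1 − f)q, where q = 1 − (1 − e^(−λ))/λ = 1 − L/λ.

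| L | λ | q (f = 0) | f = 0.3 |
|---|---|---|---|
| 5% | 0.0513 | 2.5% | 32% |
| 10% | 0.1054 | 5.1% | 34% |
| 20% | 0.2231 | 10.4% | 37% |

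A simulation under the same assumptions agrees to within rounding. These are shares of events lost from the cohort. They are not estimates of bias in a hazard ratio.

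**The case against.** The strongest reply is that each criterion has a harmless reading that fits the rest of the protocol. The start rule on valid data, the year of non-use and the third bullet all need a year of earlier records, so the first bullet may be a clumsily worded look-back. The explicit switch rules show that switchers are meant to be kept and censored, which favours reading the fourth bullet as earlier use. This stands as evidence of intent. It does not remove the defect: the word used in both places is follow-up, the fourth bullet has no window beside one that does, and the harmless reading has to be inferred.

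A reader might infer that the first bullet removes early harms in general. It does not. It concerns data available in the source, so a patient with an early non-fatal event who stays registered is kept. Only those who die, leave or reach the end of data within a year would be lost.

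A reader might also infer that the rules make the drug look safer or shift the hazard ratio by a given amount. The documents do not support that. Both criteria apply to users and non-users. The protocol gives no mortality, departure or switching rates by group, nor event rates among switchers. For WP2 and WP4, events in users before six months of continued prescriptions are outside follow-up in any case.

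**Conclusion.** The point holds as a defect of wording that can produce a wrong cohort. Two eligibility criteria lack an anchor at entry. The first, taken literally, contradicts censoring item a. The fourth, if it covers use after entry, contradicts censoring item d in both lists and removes non-users who later start another drug.

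It is not established that selection on later events was intended or carried out; a look-back is a plausible intention for the first bullet, and earlier use for the fourth. Neither the direction nor the size of any effect on the hazard ratios can be fixed from the protocol. The percentages above rest wholly on assumed rates and show only how many events the literal first rule could take out.

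**What to change.** 1. Reword the first exclusion bullet, and the matching line in the Summary of Research, to require at least one year of registration with valid data before the index date, with no minimum follow-up after it.
2. Limit the fourth bullet to use of another anti-osteoporosis drug on or before the index date.
3. Leave later death and departure to the censoring rules and the competing-risk analysis. Keep later initiation of another anti-osteoporosis drug as a censoring event, worded so that it applies to non-users as well as users.
4. Confirm which reading the cohort code uses.

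The cost is a few lines of protocol text and no new data. Cohort selection, matching and analysis need to be re-run only if the code applied either criterion to time after entry or left non-users uncensored when they started another drug.
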